4. STUDY DESIGN

4.1. Overall Design

This is a Phase 2, multicentre, randomized, double-blind, parallel group, placebo-controlled study of GSK2831781 in participants with moderate to severe active UC. This study will investigate the safety and tolerability, efficacy, dose-response, PK and PD of GSK2831781. In addition, the study will investigate SC dosing during the Extended Treatment Phase.

Following the Induction Phase (up to Week 10), participants who respond will enter a double-blind Extended Treatment Phase until Week 30, with Follow-Up to Week 42. Non-

Responders identified following the Week 10 assessment will move to Open Label Treatment, consisting of Induction (Weeks 12 to 22) an Open Label Extended Treatment Phase (Weeks 22 to 42) and a Follow-Up to Week 54 (see Section 4.1.2).

[figure not shown]
At the start of the study, participants will be randomised to GSK2831781 450 mg or placebo in a 2:1 ratio. When an appropriate number of participants have been randomised in these two arms for the futility interim analysis (Interim Analysis 3, See Section 9.5), randomisation to all dose regimens (GSK2831781 450 mg, 300 mg 150 mg, 45 mg or placebo) will be opened in a 2:3:3:3:2 ratio. No pause in recruitment is planned, although study recruitment may be paused for internal decision making at the Sponsor's discretion.

A number of interim analyses will be performed during the study, where the DRC will review unblinded data for decision-making purposes (see Section 9.5 for further details).

In line with routine pharmacovigilance, an internal GSK Safety Review Team (SRT) (which will include a subset of the 204869 study team) will review blinded safety data, including clinical laboratory parameters and adverse events, at appropriate intervals during the period of study conduct.

An overview of the patient journey for the study is shown in Figure 1 and described below.

Figure 1 Participant journey

4.1.1. Double-Blind Treatment

[figure not shown]
Following informed consent, the screening period for participants is 35 days. Eligible participants, determined by entry criteria including the baseline centrally read endoscopy (endoscopy to be completed no earlier than Day -14), will be randomised on either Day 1 or Day -1, and commence 10 weeks of blinded treatment in the Double Blind Induction Phase (IP).

At Week 10, all participants will undergo an Induction Assessment, including centrally read endoscopy. Following the endoscopy, the Responder status (see [Appendix 7](#), Section [10.7](#)), as identified by the results of the central assessment of clinical response and implemented in the eCRF, will be communicated to sites prior to the Week 12 visit.

Participants identified as Responders who received GSK2831781 during Induction will then receive 300 mg GSK2831781 subcutaneously (SC) every four weeks during the double-blind Extended Treatment Phase (ETP), from Week 14 until Week 26. Responders in the placebo group during Induction will continue to receive placebo SC every four weeks in the double-blind ETP ([Figure 2](#)). A mandatory corticosteroid taper (if applicable) will begin at Week 12, described in Section [6.6.1.1](#).

At Week 30, all participants in the Double-Blind ETP will undergo an Assessment, including centrally read endoscopy. Subsequently, all participants will remain in study, but off treatment, to Week 42 in the 12-week Follow-Up phase.

Figure 2 Double-blind ETP dosing regimen (for Responders only)

4.1.2. Open Label Treatment for Non-Responders

Participants who have not attained clinical response, determined following a centrally read endoscopy at Week 10 (calculated centrally through the eCRF), will be assigned to Open Label Treatment. This offers the opportunity to characterise participants who may respond slower to treatment, as well as providing participants who have not responded on their randomized dose regimen the opportunity to receive GSK2831781 at the highest dose. The total duration of open label treatment will be up to an additional 30 weeks of treatment

[figure not shown]
(Week 12 to Week 42) and a 12-week Follow-Up (Figure 3).

Participants who have not attained clinical response, determined following a centrally read endoscopy at Week 22 (calculated centrally through the eCRF), will discontinue study treatment and are still required to attend a Follow-Up visit approximately 16 weeks from the last dose event.

Participants identified as Responders will then receive 300 mg GSK2831781 SC every four weeks during the Open Label Extended Treatment Phase from Week 22 until Week 42. A mandatory corticosteroid taper (if applicable) will begin at Week 24, described in Section 6.6.1.1.

Subsequent to Week 42, all Open Label Extended Treatment Phase participants will remain in study, but off treatment, to Week 54 in a 12-week Follow-Up phase.

Figure 3 Open Label Treatment for Non-Responders at Week 10

4.1.3. Type and number of participants

Participants with moderate to severe active UC as defined by a 4-domain (Complete) Mayo score of 6-12 at screening, including a centrally read Mayo endoscopic score of ≥ 2 within 14 days of randomization (Day 1), will be randomised into the study (see Section 5, for full list of inclusion/exclusion criteria). Participants will be stratified first by ethnicity (Japanese or non-Japanese). Non-Japanese participants will then be further stratified according to prior treatment (advanced therapy naïve, experienced a single class of advanced therapy, or experienced multiple classes of advanced therapies [advanced

therapies include anti-TNF therapies, anti-integrin therapies, anti-IL-12/23 monoclonal antibodies, and JAK inhibitors]).

Approximately 242 participants will be randomly assigned to study intervention under the assumption that a proportion will not receive all planned doses up to Week 10 and/or have an incomplete Week 10 Complete 4-domain Mayo score assessment. If the attrition rate is higher than planned for (e.g., 15% or more) then additional participants, up to a maximum of 320, may be recruited. At the start of the study, participants will be randomised to GSK2831781 450 mg and Placebo in a 2:1 ratio. When an appropriate number of participants have been randomised in these two arms for the interim analysis (Interim Analysis 3, See Section 9.5), randomisation to all dose regimens (GSK2831781 450 mg, 300 mg, 150 mg, 45 mg or Placebo) will be opened. See Section 6.4 for the randomisation ratios.

No pause in recruitment to the study is planned whilst interim analyses are conducted, although recruitment into the study may be paused for internal decision making at the Sponsor's discretion. At appropriate interim analyses a sample size re-estimation may be conducted, to ensure that sufficient participants are recruited. The randomisation will be stratified to ensure participants will be appropriately represented across the dose regimens and placebo. The maximum number of randomized participants will be 320 (see Section 9.2.2 for further details).

The proposed SoA for the study, including the Open Label Treatment, can be seen in Section 1.3.

4.2. Scientific Rationale for Study Design

This is the first study of GSK2831781 in participants with moderate to severe active UC, and the first repeat dose study. There are two primary objectives, the first of which is to evaluate the safety and tolerability of repeat doses GSK2831781. The second primary objective is to characterise the efficacy dose-response in the Induction Phase of GSK2831781 in patients with moderate to severe active UC.

The placebo group is required for a valid evaluation of adverse events attributable to GSK2831781 treatment versus those independent of GSK2831781 treatment. The placebo participants will also serve as controls for the biomarker and efficacy assessments. Participants randomised to receive placebo during the Induction Phase who have not responded by the Induction Assessment (Week 10) will have opportunity to access Open Label treatment with GSK2831781 450 mg IV.

The endpoint chosen for primary characterisation of the dose-response is the change from baseline in Mayo score (See Appendix 7, Section 10.7) at Week 10. This will be evaluated alongside the key secondary endpoint of endoscopic mucosal healing. Longitudinal data demonstrate that patients who attain mucosal healing have a superior long-term prognosis, including lower risk of future surgery and hospitalisation, need for systemic steroids, and development of colorectal cancer [Rutter, 2004]. Patient-reported outcomes are also included in the secondary and exploratory analyses.

In addition to endoscopic and symptomatic assessments, other key endpoints contributing to an understanding of whether GSK2831781 successfully ameliorates mucosal inflammation are being undertaken, including: histological, immunohistochemical and transcriptomic assessment of gut biopsies; levels of faecal calprotectin; and C-reactive protein (CRP) concentrations in blood. Further exploratory endpoints include characterisation of PK and efficacy with a single dose level of subcutaneous GSK2831781 in the Extended Treatment Phase, to determine applicability of this dosing route in future studies.

Participants will be followed for 16 weeks after the last administration of GSK2831781. Due to the non-linear nature of the PK and limited number of observations in the final phase, the terminal half-life could not be determined in the FTIH study 200630. However, the data from this study show that after dosing at 5 mg/kg IV (470 mg on average), the mean plasma concentration of GSK2831781 at Day 85 (i.e. 12 weeks after dosing) had dropped to 0.5 µg/mL, from a mean Cmax of 162 µg/mL, and in 2 out of 6 participants the concentration had dropped below the limit of quantification (10 ng/mL). At Day 121 (i.e. 17 weeks after dosing; next time point for PK), the concentrations in all participants who had received 5 mg/kg had dropped below the limit of quantification. Since only very limited accumulation is expected for monoclonal antibodies in general and, based on population PK modelling of the data from study 200630, a wash out period of 16 weeks after the last administration has been selected as a sufficient time for washout and determination of repletion of LAG3⁺ cells.

A key feature of the study is that there will be a number of interim analyses that may be performed, which will include the assessment of PK and an assessment of futility (see Section 9.5 for further details).

4.3. Justification for Dose

4.3.1. Double-Blind Induction Phase

The top dose will be 450 mg IV at Day 1 (Week 0), Day 15 (Week 2), Day 43 (Week 6) and Day 71 (Week 10). Simulations using a PK/PD model that was developed using PK and cell depletion data in blood from the FTIH study (Study 200630), and LAG3⁺ cell numbers from colon [Slevin, 2018] show that at a dosing interval of 4 weeks, this dose is predicted to reduce LAG3⁺ T cells (memory compartment) in blood to ~5%, and in colon to 5-20% of baseline levels as measured in patients with active UC.

The dosing interval is 4-weekly, except for the first 2 doses, which will be 2 weeks apart. This is predicted to achieve the maximum reduction in LAG3⁺ T cells faster, particularly in colon.

The maximum dose in the FTIH study was 5 mg/kg. Since the average weight of the participants was 94.38 kg in that treatment group (range of 85.3-108, N=6), on average the administered dose was 470 mg, which is similar to the proposed top dose of 450 mg IV. The population PK model predicts an average Cmax of 204 µg/mL and AUC(0-4wks) of 37 mg.hr/mL at Week 10. In the FTIH study, Cmax ranged between 120-230 µg/mL and AUC(0-t) ranged between 33-59 mg.hr/mL. Therefore, it is expected that the exposure at

the top dose in the current study will be similar to the observed exposure in FTIH study at 5 mg/kg single dose IV. Additionally, the proposed starting dose of 450 mg (~6.4 mg/kg for 70 kg participant) is 15.6x lower than the NOAEL (100 mg/kg/week, highest dose tested) from the 26-week GLP toxicity study in monkey, and the predicted mean Cmax and AUC are 15.2x and 12.1x lower, respectively.

For characterising the dose-response relationship, three further dose levels are included: 300 mg, 150 mg and 45 mg, all administered at the same time points as 450 mg. At the lowest dose of 45 mg, PK/PD modelling predicts only limited depletion of LAG3⁺ T cells in colon, and in blood to about 25-50%.

4.3.2. Double-Blind Extended Treatment Phase (ETP)

All participants who responded during the double-blind Induction Phase (see Section 4.1) will be dosed during the ETP via the subcutaneous route. It is anticipated in the longer term that SC administration will be preferable, and lower doses may be required to maintain target depletion. This is based on clinical experience with other mAbs in UC (for example, Infliximab and Vedolizumab), and the biology of the disease (after successful induction treatment, the elevated levels of LAG3⁺ cells in the colon are expected to be reduced). Therefore, the dose during the double-blind ETP will be 300 mg SC every 4 weeks. For participants in the 45 mg or 150 mg cohorts who respond in the Induction Phase, this may represent a dose escalation; however, this is still considered justified to explore the potential to achieve even more clinically meaningful responses and deep remission.

4.3.3. Open Label Treatment

All participants who did not respond during the double-blind Induction Phase will receive 450 mg IV at Weeks 12, 14, 18 and 22 (Open Label Induction Phase), followed by 300 mg SC every 4 weeks from Week 26-38 (Open Label Extended Treatment Phase). Since only minimal (further) accumulation of GSK2831781 is expected, continuing treatment at 450 mg IV for Non-Responders who might have received this dose during the double-blind Induction Phase as well will result in only limited, if any, increases in exposure.

4.4. End of Study Definition

A participant is considered to have completed the study if he/she has completed all phases of the study including the last scheduled assessment shown in the SoA (Section 1.3).

Participants who withdraw from the study early should be encouraged to complete all visits for that specific phase as set out in the SoA (Section 1.3); however, if this is not possible at a minimum participants will be asked to complete all assessments at both the Early Withdrawal visit and a Follow-Up visit approximately 16 weeks after the last dose (Section 7.2) to ensure participant monitoring following drug wash out.

The end of the study is defined as the date of the last visit of the last participant in the study.

5. STUDY POPULATION

Prospective approval of protocol deviations to recruitment and enrolment criteria, also known as protocol waivers or exemptions, is not permitted.

5.1. Inclusion Criteria

Participants are eligible to be included in the study only if all the following criteria apply:

AGE and WEIGHT

 Participant must be 18 years of age or older and >40kg at the time of signing the informed consent.
TYPE OF PARTICIPANT AND DISEASE CHARACTERISTICS

Participants who have a:
 
 Diagnosis of ulcerative colitis, established at least 3 months prior to screening, as documented by diagnostic sigmoidoscopy or colonoscopy, and biopsy. Complete 4-domain Mayo Score of 6 to 12, with disease extending $\geq 15\text{cm}$ from the anal verge, with a centrally read endoscopic subscore of ≥ 2 at screening endoscopy, and a rectal bleeding subscore ≥ 1. A history of at least one of the following: 
 Inadequate response to, loss of response to, or intolerance to azathioprine or mercaptopurine (including thiopurine methyltransferase (TPMT) and NUDT15 genetic mutations precluding use), cyclosporin, tacrolimus or methotrexate. Inadequate response to, loss of response to, intolerance to, or demonstrated dependence on oral corticosteroids. Inadequate response to, loss of response to, or intolerance to at least one approved advanced therapy for UC, including anti-TNF therapies, anti-integrin therapies, anti-IL-12/23 monoclonal antibodies or JAK inhibitors. Surveillance colonoscopy (performed according to local standards) within 12 months of screening (or during screening, if required) for participants with: 
 Pancolitis of >8 years duration; or Patients with left-sided colitis of >12 years duration; or For patients for whom this criterion does not apply, colorectal cancer surveillance should be undertaken according to local or national guidelines for patients with age ≥ 50, or with other known risk factors for colorectal cancer.

SEX

6. Male and Female participants:

Both male and female participants are eligible to participate.

A female participant is eligible to participate if she is not pregnant, not breastfeeding, and at least one of the following conditions applies:

- Not a woman of childbearing potential (WOCBP), see Section [10.4.1](#).

OR

- A WOCBP who agrees to use a highly effective contraceptive method for at least 4 weeks prior to dosing, until the Follow-Up visit. See Section [10.4.2](#).

INFORMED CONSENT

7. Capable of giving signed informed consent as described in Section [10.1.3](#) which includes compliance with the requirements and restrictions listed in the informed consent form (ICF) and in this protocol.

5.2. Exclusion Criteria

Participants are excluded from the study if any of the following criteria apply:

MEDICAL CONDITIONS

1. Participants with a current diagnosis of indeterminate colitis, inflammatory bowel disease-unclassified, Crohn's disease, infectious colitis, or ischaemic colitis.
2. Participants with fulminant ulcerative colitis (as defined by 6 bloody stools daily AND 1 or more of: i) body temperature $\geq 100.4^{\circ}\text{F}$ (or 38°C) or ii) heart rate >90 beats per minute), or toxic megacolon.
3. Prior extensive colonic resection, subtotal or total colectomy, or proctocolectomy, or planned surgery for UC.
4. Participants with any uncontrolled medical conditions, other than active UC, that in the opinion of the Investigator put the participant at unacceptable risk or interfere with study assessments or integrity of the data. Other medical conditions should be stable at the time of screening and be expected to remain stable for the duration of the study.
5. Unstable lifestyle factors, such as alcohol use to excess or recreational drug use, to the extent that in the opinion of the Investigator they would interfere with the ability of a participant to complete the study.
6. An active infection or a history of serious infections as follows:


 - Use of antimicrobials (antibacterials, antivirals, antifungals or antiparasitic agents) for an infection within 30 days before first dose (topical treatments may be allowed at the Medical Monitor's discretion). - A history of opportunistic infections within 1 year of screening (e.g. Pneumocystis jirovecii, aspergillosis or CMV colitis). This does not include infections that may occur in immunocompetent individuals, such as fungal nail infections or vaginal candidiasis, unless it is of an unusual severity or recurrent nature. - Recurrent or chronic infection or other active infection that, in the opinion of the Investigator, might cause this study to be detrimental to the patient. - Symptomatic herpes zoster within 3 months prior to screening. - History of tuberculosis (active or latent), irrespective of treatment status. - A positive diagnostic TB test at screening (defined as a positive QuantiFERON test). In cases where the QuantiFERON test is indeterminate, the participant may have the test repeated once and if their second test is negative they will be eligible. In the event a second test is also indeterminate, the Investigator has the option to undertake PPD testing. If the PPD reaction is <5 mm, then the participant is eligible. If the reaction is ≥ 5 mm, or PPD testing is not undertaken, the participant is not eligible. - Positive Clostridium difficile toxin test during screening. However, rescreening can be undertaken following successful treatment.
7. Current or history of chronic liver or biliary disease (with the exception of Gilbert's syndrome, asymptomatic gallstones or uncomplicated fatty liver disease).
8. Hereditary or acquired immunodeficiency disorder, including immunoglobulin deficiency (unless the participant has a documented history of selective IgA deficiency).
9. A major organ transplant (e.g. heart, lung, kidney, liver, pancreas) or haematopoietic stem cell/marrow transplant.
10. Any planned major surgical procedure during the study.
11. A history of malignant neoplasm within the last 5 years, except for adequately treated non-metastatic basal or squamous cell cancers of the skin (within 1 year) or carcinoma in situ of the uterine cervix (within 3 years) that has been fully treated and shows no evidence of recurrence.

PRIOR/CONCOMITANT THERAPY
12. A change in dose of oral sulfasalazine or aminosalicylate within 2 weeks prior to baseline endoscopy.
13. Greater than 20 mg/day oral prednisolone (or equivalent, see SRM), or a change in dose of corticosteroid within 2 weeks prior to baseline endoscopy, or anticipated

inability to maintain a stable dose of corticosteroids (≤ 20 mg oral prednisolone or equivalent, see SRM) until Week 12.

14. Topical (rectal) corticosteroids or topical (rectal) aminosalicylate within 2 weeks prior to baseline endoscopy.
15. Initiation or a change in dose of mercaptopurine or azathioprine (including initiation or discontinuation of allopurinol) or methotrexate within 8 weeks prior to baseline endoscopy.
16. Treatment with ciclosporin, tacrolimus or thalidomide within 4 weeks prior to baseline endoscopy.
17. Treatment with an anti-TNF biologic within 8 weeks prior to baseline endoscopy, anti-integrin or anti-IL-12/23 biologics within 12 weeks prior to baseline endoscopy, or a JAK inhibitor within 4 weeks prior to baseline endoscopy.
18. A history of inadequate response, loss of response, or intolerance to more than three classes of approved advanced therapies for UC (including anti-TNF therapies, anti-integrin therapies, anti-IL-12/23 monoclonal antibodies, or JAK inhibitors; but excluding exposure within a clinical trial setting), of which participants must not have had inadequate response (primary non-response) to more than two classes.
19. Received faecal microbiota transplantation within 4 weeks prior to baseline endoscopy.
20. Received live vaccination within 4 weeks of Day 1 or plan to receive during the study until Follow-Up.

PRIOR/CONCURRENT CLINICAL STUDY EXPERIENCE

21. The participant has participated in a clinical trial and has received an investigational product within the following time period prior to the screening endoscopy day in the current study:
 - a. Biologics: 3 months, 5 half-lives, or twice the duration of the biological effect of the investigational product (whichever is longer);
 - b. New Chemical Entities (NCEs): 30 days, 5 half-lives or twice the duration of the biological effect (whichever is longer).

DIAGNOSTIC ASSESSMENTS*

22. Absolute neutrophil count $<1.5 \times 10^9/L$ or a haemoglobin $<80 \text{ g/L}$ or lymphocyte count $<0.8 \times 10^9/L$.
23. Estimated glomerular filtration rate (GFR) by Chronic Kidney Disease Epidemiology Collaboration equation (CKD-EPI) calculation $<60 \text{ ml/min}/1.73\text{m}^2$ at screening.
24. ALT $>2 \times \text{ULN}$ and bilirubin $>1.5 \times \text{ULN}$ (isolated bilirubin $>1.5 \times \text{ULN}$ is acceptable if bilirubin is fractionated and direct bilirubin $<35\%$) at screening.

- 25. Other clinically significant abnormalities of laboratory assessments, as judged by the Investigator and/or GSK Medical Monitor, that could affect the safety of the participant, or the interpretation of the data from the study.
- 26. Presence of hepatitis B surface antigen (HBsAg) or Hepatitis B core antibody (HBcAb), or positive hepatitis C antibody result at screening (NB. participants with positive Hepatitis C antibody due to prior resolved disease can be enrolled only if a confirmatory negative Hepatitis C RNA test is obtained).
- 27. Positive serology for HIV at screening.
- 28. Where participation in the study would result in donation of blood or blood products in excess of 500 mL within 3 months.
- 29. QTc >450 msec or QTc >480 msec for participants with bundle branch block at screening and Day 1. The QTc is the QT interval corrected for heart rate according to either Bazett's formula (QTcB), Fridericia's formula (QTcF), or another method, machine or over read.**

* Retesting, in the case of potentially spurious results or sample handling errors, is allowed during the screening period.

** Same correction to be used throughout the study.

OTHER EXCLUSION CRITERIA

- 30. Participants with hypersensitivity to GSK2831781 or any excipients in the clinical formulation of GSK2831781 (See GSK2831781 Investigator Brochure).

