10.6. Appendix 6: Liver Safety: Required Actions and Follow-up Assessments Guidelines

Phase II liver chemistry stopping and increased monitoring criteria have been designed to assure participant safety and evaluate liver event aetiology

Phase II liver chemistry stopping criteria and required follow up assessments

Liver Chemistry Stopping Criteria	
ALT-absolute	ALT \geq 5xULN
ALT Increase	ALT \geq 3xULN persists for \geq 4 weeks
Bilirubin^{1, 2}	ALT \geq 3xULN and bilirubin \geq 2xULN (>35% direct bilirubin)
INR²	ALT \geq 3xULN and INR >1.5
Cannot Monitor	ALT \geq 3xULN and cannot be monitored weekly for 4 weeks
Symptomatic³	ALT \geq 3xULN associated with symptoms (new or worsening) believed to be related to liver injury or hypersensitivity
Required Actions and Follow up Assessments	
Actions	Follow Up Assessments

 • Immediately discontinue study intervention. • Report the event to GSK within 24 hours. • Complete the liver event CRF and complete an SAE data collection tool if the event also meets the criteria for an SAE². • Perform liver chemistry event follow-up assessments. • Monitor the participant until liver chemistries resolve, stabilize, or return to within baseline (see MONITORING below). • Do not restart/rechallenge participant with study treatment unless allowed per protocol and GSK Medical Governance approval is granted (see below). • If restart/rechallenge not allowed per protocol or not granted, permanently discontinue study treatment and continue 	
 • Viral hepatitis serology⁴. • Obtain INR and recheck with each liver chemistry assessment until the transaminases values show downward trend. • Obtain blood sample for pharmacokinetic (PK) analysis, as soon as possible, and at least within 7 days⁵. • Serum creatine phosphokinase (CPK) and lactate dehydrogenase (LDH). • Fractionate bilirubin, if total bilirubin \geq2xULN. • Obtain complete blood count with differential to assess eosinophilia. • Record the appearance or worsening of clinical symptoms of liver injury, or

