ALT \geq 3xULN and <5xULN and bilirubin <2xULN, without symptoms believed to be related to liver injury or hypersensitivity, and who can be monitored weekly for 4 weeks	
 Notify the GSK Medical Monitor within 24 hours of learning of the abnormality to discuss participant safety. Participant can continue study intervention. Participant must return weekly for repeat liver chemistries (ALT, AST, alkaline phosphatase, bilirubin) until they resolve, stabilise or return to within baseline. If at any time participant meets the liver chemistry stopping criteria, proceed as described above. If, after 4 weeks of monitoring, ALT <3xULN and bilirubin <2xULN, monitor participants twice monthly until liver chemistries normalize or return to within baseline.

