## 15.8. Appendix 8: Values of Potential Clinical Importance

### 15.8.1. Laboratory Values

Haematology				
Laboratory Parameter	Units	Category	Clinical Concern Range	
			Low Flag (< x)	High Flag (>x)
Hematocrit	Ratio of 1	Male	0.201	0.599
		Female	0.201	0.599
Hemoglobin	g/L	Male	80	180
		Female	80	180
		Δ from BL	↓25	
Lymphocytes	Gl/L		0.8	
Neutrophils Absolute	Gl/L		1.5	
Platelet Count	Gl/L		100	550
White Blood Cell Count (WBC)	Gl/L		3	20
Eosinophil	Gl/L			>=1

Clinical Chemistry				
Laboratory Parameter	Units	Category	Clinical Concern Range	
			Low Flag (< x)	High Flag (>x)
Albumin	mmol/L		30	55
Calcium	mmol/L		2	2.75
Creatinine	mmol/L	Δ from BL		↑26
Glucose	mmol/L		3.5	7.9
eGFR	ml/min/1.73m 		60	
Potassium	mmol/L		3	5.5
Sodium	mmol/L		130	150
Total protein	g/L		50	85
Urea nitrogen	mmol/L			10.5
CRP	Mg/L			30

Liver Function				
Test Analyte	Units	Category	Clinical Concern Range	
ALT/SGPT	U/L	High	≥ 2x ULN	
AST/SGOT	U/L	High	≥ 2x ULN	
AlkPhos	U/L	High	≥ 2x ULN	
T Bilirubin	μmol/L	High	≥ 1.5xULN	
T. Bilirubin + ALT	μmol/L U/L	High	1.5xULN T. Bilirubin + ≥ 2x ULN ALT	

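### Exclusion 24 joins its ALT and bilirubin limits with 'and', so its bilirubin exception has no effect and a raised ALT alone, even at the 5xULN stopping value, is outside the numeric criterion

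*Protocol*

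**What the plan says.** Protocol Section 5.2, exclusion 24, has two parts. The main clause joins ALT above 2xULN and bilirubin above 1.5xULN with 'and', at screening. The parenthesis says an isolated bilirubin above 1.5xULN "is acceptable if bilirubin is fractionated and direct bilirubin" is below 35%.

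The related provisions are:

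- **Exclusion 22** (same section) lists its neutrophil, haemoglobin and lymphocyte limits joined by 'or', so each excludes on its own.
- **SAP Section 15.8.1** flags ALT at 2xULN or more and total bilirubin at 1.5xULN or more in separate rows. A further row covers the joint condition, "1.5xULN T. Bilirubin + ≥ 2x ULN ALT".
- **Protocol Appendix 6** (Section 10.6) makes ALT of 5xULN or more a stopping criterion with no bilirubin condition. The required action is "Immediately discontinue study intervention".
- **The same appendix**, for ALT from 3 to below 5xULN with bilirubin below 2xULN, no relevant symptoms and feasible weekly monitoring, says "Participant can continue study intervention".

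**The concern.** An exception is needed only where the rule would otherwise apply. Under a strict 'and', a participant with raised bilirubin but ALT at or below 2xULN is never caught, so there is nothing for the parenthesis to except. Its evident implication is that isolated bilirubin with a direct fraction of 35% or more, or never fractionated, is not acceptable. The rule does not enforce that.

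The same 'and' means no level of ALT excludes on its own. A participant whose screening ALT already meets the protocol's own stopping rule would not fail the liver criterion if bilirubin were normal. Entry would then depend on a judgement or on another diagnosis.

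The sentence therefore supports two incompatible rules, and sites can apply it differently. Exact wording matters because waivers of entry criteria are not permitted (Protocol Sections 5 and 8) and the SAP (Section 4.5) summarises and lists inclusion/exclusion deviations separately. Two sites could enrol different patients, or classify the same patient differently as a deviation.

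**Working it through.** The plan gives no figure to reproduce; the check is of the logic.

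**Inputs.** ALT limit 2xULN, bilirubin limit 1.5xULN and direct fraction 35% (exclusion 24); stopping value ALT 5xULN (Appendix 6).

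**Rules compared.**

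- Literal: excluded if ALT > 2 and bilirubin > 1.5 (both xULN).
- Separate limits: excluded if ALT > 2, or if bilirubin > 1.5 and it is not the case that bilirubin was fractionated with direct < 35%.

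**Panels.** These are chosen for illustration: ALT 1, 2.5, 3 or 5 xULN, crossed with bilirubin 1 xULN, or 2 xULN with direct 20%, direct 50% or not fractionated. That gives 4 x 4 = 16. Each cell shows literal / separate; E = excluded, – = not excluded.

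| ALT (xULN) | Bili 1 | Bili 2, direct 20% | Bili 2, direct 50% | Bili 2, not fractionated |
|---|---|---|---|---|
| 1 | – / – | – / – | – / E | – / E |
| 2.5 | – / E | E / E | E / E | E / E |
| 3 | – / E | E / E | E / E | E / E |
| 5 | – / E | E / E | E / E | E / E |

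- Literal: 3 ALT values x 3 bilirubin states = 9 excluded.
- Separate limits: 3 x 4 = 12, plus 2 isolated-bilirubin panels = 14 excluded.
- Difference: 14 − 9 = 5. These are ALT 2.5, 3 and 5 with bilirubin 1, and ALT 1 with bilirubin 2 (direct 50%; not fractionated).
- No panel excluded by the literal rule becomes eligible under separate limits.
- With direct 20% and ALT 1 both rules allow entry, so nothing turns on that case.

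**Does the exception do anything?** A second grid used ALT 1, 2.5, 4, 5 and 8 xULN, bilirubin 1 and 2.5 xULN, and direct 20% and 50% (5 x 2 x 2 = 20 profiles). Each rule was applied with and without the exception. Under 'and' the exception changed 0 of 20 results. Under 'or' it changed 1 of 20 (ALT 1, bilirubin 2.5, direct 20%).

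**Against the stopping rules.** The second grid was also checked against ALT of 5xULN or more, and ALT of 3xULN or more with bilirubin of 2xULN or more (direct above 35%). Under 'and', the profiles with ALT 5 and 8 and bilirubin 1 are not excluded although they meet a stopping value. Under 'or', no profile at a tested stopping value escapes exclusion. In the 16-panel grid, 1 of the 5 differing panels (ALT 5, bilirubin 1) is at a stopping value.

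**Other protection.**

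| Provision | What it rests on |
|---|---|
| Exclusion 4 | Investigator's opinion on uncontrolled conditions |
| Exclusion 7: "Current or history of chronic liver or biliary disease" | A diagnosis; uncomplicated fatty liver is allowed |
| Exclusion 25 | Judgement of the Investigator and/or Medical Monitor |
| Exclusion 26 | Hepatitis B or C serology |
| Day 1 pre-dose chemistry (SoA) | No numeric liver limit for entry is stated |

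None sets an ALT limit.

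**The case against.** The strongest reply is that the criterion resists the strict reading. Because the parenthesis makes sense only if bilirubin can exclude alone, a site may take the sentence as a list of two disqualifying findings, with a carve-out for unconjugated bilirubin that fits the Gilbert's syndrome exception in exclusion 7. On that reading there is no ALT gap and only loose drafting. This supports separate limits as the likely intention, but the text does not state it.

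The supporting evidence can be turned round. The 'or' in exclusion 22 shows the authors used 'or' when they meant it, so 'and' could be deliberate. SAP Section 15.8.1 sets reporting flags, not entry limits. Neither source settles intent.

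If a joint rule was intended, admitting isolated ALT above 2 and below 5xULN is compatible with Appendix 6, which can let dosing continue from 3 to below 5xULN under monitoring. That stands, and no conflict with the stopping rules is claimed there. The conflict is confined to ALT of 5xULN or more.

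The backstops, with the Section 8 requirement to review all screening results, make dosing such a participant unlikely. That also stands, but they do not supply the missing limit. The panel counts reflect the grid chosen, not participants or risk, and divergent site practice is possible rather than shown. The eCRF and SRM wording is not available.

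Finally, SAP Section 2.1 records the decision to terminate the study on 14 January 2021. That limits the practical benefit of an amendment to this trial; it does not alter the defect in the protocol text.

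**Conclusion.** The point holds. Under the literal wording the bilirubin exception is inert, and ALT above 2xULN with bilirubin at or below 1.5xULN is outside the numeric criterion, including values at which the protocol stops treatment. In size it is a defect in an operative safety threshold: 9 against 14 of 16 illustrative panels, with one of the five differing panels at a stopping value. The number of participants affected cannot be derived from the documents.

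The conclusion rests on reading 'and' as requiring both conditions. If separate limits were meant, the wording fails to say so; if the joint rule was meant, the parenthesis is redundant and there is no ALT ceiling. Either way the sentence should be corrected. The other exclusions limit the likely harm, so this is a correction that should be made rather than a threat to the trial's conclusions. It bears on no estimand or planned efficacy analysis.

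**What to change.** State the limits separately, for example:

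> ALT >2xULN, or bilirubin >1.5xULN (an isolated bilirubin >1.5xULN is allowed only if fractionated with direct bilirubin <35%), at screening.

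If the joint rule was intended, delete the parenthesis and add a separate upper ALT limit below 5xULN.

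The text change is small, but it alters an exclusion criterion. It needs a protocol amendment with IEC/IRB approval (Protocol Section 10.1.1) and matching eCRF wording. No new test is required, because total and direct bilirubin are already in the central chemistry panel (Protocol Appendix 2, Table 7). Where sites had applied 'and' literally, eligibility narrows slightly: ALT above 2xULN with normal bilirubin, and isolated bilirubin that is unfractionated or has a direct fraction of 35% or more, become ineligible. With this study terminated, the remaining practical use is to settle one reading for classifying eligibility deviations and to keep the wording out of later protocols.
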